## 6.4 Withdrawal of individual subjects

Subjects can leave the study at any time for any reason if they wish to do so without any consequences. The investigator can decide to withdraw a subject from the study for urgent medical reasons.

## 6.5 **Replacement of individual subjects after withdrawal**

After withdrawal, individual participants will not be replaced.

## 6.6 Follow-up of subjects withdrawn from treatment

Dropouts will be contacted by phone and asked to fill out the remaining questionnaires to supply the researchers with a post measurement and follow-up. Dropouts will be reminded that they are free to refuse.

## 6.7 **Premature termination of the study**

There are no criteria for premature termination of the study.

# 7. SAFETY REPORTING

#### 7.1 Temporary halt for reasons of subject safety

In accordance to section 10, subsection 4, of the WMO, the sponsor will suspend the study if there is sufficient ground that continuation of the study will jeopardise subject health or safety. The sponsor will notify the accredited METC without undue delay of a temporary halt including the reason for such an action. The study will be suspended pending a further positive decision by the accredited METC. The investigator will take care that all subjects are kept informed.

#### 7.2 AEs, SAEs and SUSARs

## 7.2.1 Adverse events (AEs)

Adverse events are defined as any undesirable experience occurring to a subject during the study, whether or not considered related to the mindfulness training. All adverse events reported spontaneously by the subject or observed by the investigator or his staff will be recorded.

#### 7.2.2 Serious adverse events (SAEs)

A serious adverse event is any untoward medical occurrence or effect that:

- Results in death;
- Is life threatening (at the time of the event);
- Requires hospitalisation or prolongation of existing inpatients' hospitalisation;
- Results in persistent or significant disability or incapacity;
- Is a congenital anomaly or birth defect, or;
- Any other important medical event that did not result in any of the outcomes listed above due to medical or surgical intervention but could have been based upon appropriate judgement by the investigator.

We expect the number of (S)AE's during the intervention to be minimal, as the intervention is noninvasive. Adverse events or reactions that may occur during the study will be examined at each assessment by explicitly asking if people may have noticed unpleasant effects that appear to be causally related to the MBCT training. Reported adverse events related to meditation could be relaxation-induced anxiety and panic, paradoxical increases in tension, impaired reality testing, confusion, disorientation, dissociation, feeling addicted to meditation and grandiosity (Dobkin, Irving, & Amar, 2012; Shapiro, 1992). Furthermore, we will be watchful for posttraumatic stress symptoms that might arise as a result of the MBCT training, such as re-experiencing. The principal investigators will check the questionnaires on signs of (S)AE's as well. All adverse events reported spontaneously by the participant or observed by the principal investigator or his/her staff will be recorded and reported through the web portal *ToetsingOnline* to the accredited METC that approved the protocol, within 7 days of first knowledge for SAEs that result in death or are life threatening followed by a period of maximum of 8 days to complete the initial preliminary report. All other SAEs will be reported within a period of maximum 15 days after the sponsor has first knowledge of the serious adverse events.

The investigator will report all SAEs to the sponsor without undue delay after obtaining knowledge of the events, except for the following SAEs:

- An elective hospital admission.
- Relapse into a (hypo)manic or depressive episode, which is an expected event in this specific population, since 60% of BD patients relapse within two years (Miklowitz et al., 2009; Oud et al., 2016). The study of Perich et al. (2013), who conducted a RCT of MBCT for BD, found that 59% of participants in the MBCT condition and 48% in the TAU condition reported a (hypo)manic episode, while 59% in the MBCT condition and 68% in TAU reported a depressive episode over a 12 month follow-up period. In that study, the median time to

(hypo)mania relapse was 130 days for MBCT and 143 for TAU. Median time to depressive relapse was 53 days for MBCT and 46 days for TAU.

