#### 3. STUDY DESIGN

A randomized, multicenter, prospective, evaluator-blinded clinical trial of MBCT added to treatment as usual (TAU) versus TAU alone. Assessments will be conducted at baseline and at 3, 6, 9, 12, and 15 months follow-up. At the end of the study period (15 months), the participants in the TAU group will be offered MBCT as well. Three external, specialized outpatients clinics for treatment of BD, will be participating in the present study. See Figure 1 for a prospective flow chart of the study.

Figure 1. Prospective flow chart of the study

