#### 6.1.1 Main study parameter/endpoint

The primary endpoint of the study is severity of depressive symptoms at 3 months follow-up (T1), assessed with the *Inventory of Depressive Symptomatology – Clinician administered* (IDS-C; Akkerhuis, 1997). The IDS-C has good psychometric qualities (Rush, Gullion, Basco, Jarrett, & Trivedi, 1996; Trivedi et al., 2004) and will be administered by trained research assistants.

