## 6.2 Randomisation, blinding and treatment allocation

Randomisation will be performed within the datamanagement system Castor EDC. This will consist of stratified, variable block randomisation with the following stratification variables: Location (site); Gender; Depression (current versus remitted); BD type (I versus II); and number of previous episodes (<12 versus =/> 12). This system also allows for blinded (concealed) allocation such that research assistants on site can be kept blind to condition. MBCT teachers on site will be notified of the allocation to MBCT, allowing them to invite the patient to participate and coordinate further arrangements. As only assessors will be blind to treatment allocation due to the nature of the intervention, no indications for breaking the randomization code are pre-specified. In case of adverse reactions, patients are encouraged to discuss this with their MBCT teacher and responsible clinician.

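### The protocol asks about MBCT-related unpleasant effects at each assessment, but nothing keeps the question or its answers from the blinded outcome raters

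*Protocol*

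**What the plan says.** Section 3 describes the trial as follows: "A randomized, multicenter, prospective, evaluator-blinded clinical trial of MBCT added to treatment as usual (TAU) versus TAU alone". Section 6.2 limits the blinding to one group: "As only assessors will be blind to treatment allocation due to the nature of the intervention". The safeguard it names is technical: "This system also allows for blinded (concealed) allocation such that research assistants on site can be kept blind to condition".

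The primary endpoint is the IDS-C at T1, which under section 6.1.1 "will be administered by trained research assistants". Section 6.3 and Table 1 place the IDS-C, YMRS, FAST and SCID-I (depression and mania parts) at the follow-up assessments. T2 to T4 are done by telephone. Participants also complete online questionnaires at each follow-up.

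Section 7.2.2 has adverse events or reactions "examined at each assessment by explicitly asking if people may have noticed unpleasant effects that appear to be causally related to the MBCT training". It names no asker, mode or order. It adds that the principal investigators also check the questionnaires for signs of adverse events. Section 6.3 mentions a personal diary for adherence and adverse events, in the text on the MBCT arm. Table 1 has a combined row for mindfulness adherence and adverse events in its self-report block. Section 6.2 encourages patients with adverse reactions to speak to their MBCT teacher and clinician.

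**The concern.** Participants and teachers know the allocation, so the blinded rater is the design's stated protection against expectation bias in the clinician-rated outcomes. A question that presupposes the MBCT training, put on the same occasion as those ratings, invites participants to say whether they had the training. Concealed allocation in the randomisation system stops the rater from looking up the arm. It does nothing about what the participant says.

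The ratings at stake go beyond the T1 IDS-C. Later IDS-C scores enter the repeated-measures model to 15 months (section 8.1) and the 12-month effect in the cost-effectiveness ratio (section 8.2). The YMRS and FAST are secondary outcomes, and the SCID-I supplies the relapse assessment (section 6.1.2).

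**Working it through.** The check is mainly a reading of the sections side by side.

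**1. Do the question and the ratings fall on the same occasions?** Yes. Section 7.2.2 says each assessment, and Table 1 puts the IDS-C, YMRS, FAST and SCID-I at T1 to T5. At T0 the training has not begun, so T1 to T5 are what matter.

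**2. What can an answer disclose?** Under section 3 the TAU group is offered MBCT only after 15 months.
- A description of an effect of the practice points to MBCT + TAU.
- A remark about not having been in the training points to TAU.
- A plain no fits either arm, and section 7.2.2 expects few events.

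If the question were put only to MBCT participants, whoever asks would have to know the arm.

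**3. Who asks?** The text supports two readings.
- *Interview:* the investigators' check of questionnaires is described as additional to the asking. The self-report sets that section 6.3 lists by name for T0 and T5 include no adverse-event form. At T2 to T4 the telephone interview is the only staff contact described.
- *Self-report:* Table 1 puts adverse events in the self-report block, and section 6.3 has a diary.

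Neither reading is excluded, and no sentence bars the rater from asking or from seeing the answers.

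**4. What follows under each arrangement?**

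| Arrangement | T1 IDS-C | T2 to T5 ratings |
|---|---|---|
| Rater asks before the IDS-C | at risk | at risk if the same rater continues |
| Rater asks after the IDS-C | unaffected | at risk if the same rater continues |
| Self-report or other staff, rater does not see the answers | unaffected by this route | unaffected by this route |

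**5. Size.** No figure in the protocol measures rating bias, so only a what-if is possible. First, the plan's own sample size (section 4.4: effect size 0.5, two-sided alpha 0.05, power 80%, design factor 0.75, 40% loss):
- 2 × (1.960 + 0.842)² / 0.5² = 62.8, so 63 per arm
- 63 × 0.75 = 47.25, so 48 per arm
- 48 / (1 − 0.40) = 80 per arm, 160 in total, which agrees with the plan

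With 48 analysed per arm, the standard error of the difference in SD units is √(0.75 × 2 / 48) = 0.177. For an average rating bias b between arms and no true effect, the two-sided type I error is 1 − Φ(1.96 − b/0.177) + Φ(−1.96 − b/0.177).

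| Assumed b (SD) | Type I error |
|---|---|
| 0 | 5% |
| 0.1 | about 9% |
| 0.2 | about 20% |
| 0.3 | about 40% |

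The values of b are assumptions, not figures from the protocol. Each is an average over all rated participants, including those whose rater stays blind, so partial unblinding would make b smaller. The table shows how sensitive the primary test is to rating bias. It does not estimate the bias in this trial.

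**The case against.** A reader might infer that the IDS-C rater puts the question, so that the trial's own procedure undoes the blinding at every follow-up. The documents do not support that, for four reasons.
- Section 7.2.2 is in the passive voice and names no asker. An assessment in this trial includes online questionnaires as well as the interview, and Table 1 and the diary point to a possible self-report route.
- A plain no need not reveal the arm, so it does not follow that all ratings become open-label.
- If the question follows the T1 IDS-C, the primary rating is intact. Harm to later ratings then needs a further assumption, that the same rater continues.
- Any bias in SD units is assumed. Converting it to scale points would borrow an SD from the self-rated IDS in recurrent unipolar depression (section 4.4), a different instrument and population.

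All four stand, and they limit the point to a risk that the protocol leaves open. They do not remove it. None of the alternative routes says that the rater is kept out. A diary described in the text on the MBCT arm is not the same as explicit asking at each assessment. A site that followed section 7.2.2 within the interview would be complying with the protocol.

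**Conclusion.** The point holds in a limited form. Section 7.2.2 sets up an MBCT-specific question on the same occasions as the blinded ratings, and no section separates the two by person, mode or order. The evaluator blinding claimed in sections 3 and 6.2 is therefore not protected against this route. Whether it would fail in practice depends on three things the protocol does not state: whether the rater asks or sees the answers, whether the question precedes the IDS-C, and whether the same rater sees the participant again.

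The size of any bias cannot be derived from the documents. The correction is worth making because it protects the primary outcome at little cost. Confidence is moderate, because the interview reading is natural but not stated.

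**What to change.** State in sections 6.3 and 7.2.2 that:
- the MBCT-related question is put through the existing online self-report set at T1 to T5, or by staff who do not rate outcomes, and the answers are read promptly by non-rating staff;
- outcome raters neither ask about nor see training-related effects, diaries or adherence records;
- participants are asked not to disclose their arm to the rater;
- raters record any unblinding, and a guess of the arm once the T1 IDS-C is completed.

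Leaving the question to the MBCT teacher would not be enough. The course lasts eight weeks (section 5.1), while assessments run to month 15, so systematic asking would be lost for most of follow-up.

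The cost is a few lines of text, one item in the online set and two short fields for the rater. The downside is that complaints arrive by form rather than in an interview, so someone must be responsible for reading the form promptly.

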## 7.3 Follow-up of adverse events

All AEs will be followed until they have abated, or until a stable situation has been reached. Depending on the event, follow up may require additional tests or medical procedures as indicated, and/or referral to the general physician or a medical specialist. SAEs need to be reported till end of study within the Netherlands, as defined in the protocol.

## 7.4 Data Safety Monitoring Board (DSMB) / Safety Committee

It is estimated that the risk of harm is not increased when participating in this study. With regard to NFU-classification the risk is negligible. Therefore a DSMB is not needed for this study.

# 8. STATISTICAL ANALYSIS

Multilevel analysis will be used to account for the cluster-randomized design and therefore the hierarchical structure of the data, with outcome variables at the pre- and postmeasurements at the lowest level, nested within individuals, nested within treatment groups (for the intervention condition), and nested within condition (MCBT + TAU vs TAU). Any baseline parameters that may be inadvertently unequally distributed between the conditions are included as covariates. Multilevel logistic regression will be performed for dichotomous outcomes and multilevel regression analysis for normally distributed continuous outcomes. The clinical outcome data will be analysed and reported according to the CONSORT guidelines, i.e. on intention-to-treat basis. Given the anticipated drop-out, we will also analyze and report on the per-protocol group, and discuss possible differences between the two analysis sets.

Additional analyses will be performed within subgroups with and without a current depressive episode. To account for possible differences between therapy groups, we will add a random group effect. Sensitivity analyses will be conducted with different scenarios of imputed data sets, in case of missing data, to examine the influence of missing data on the pattern of outcomes.

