## 4.4 Sample size calculation

Sample size calculation is based on the estimated change in depressive symptoms form pre- to posttreatment. As we aim to include patients with all levels of depressive symptoms, we based our calculation on a previous study conducted at the Radboudumc Centre for Mindfulness (van Aalderen et al., 2012). In this study, levels of depression as assessed with the Inventory of depressive symptomatology – self-rated (IDS-SR) decreased in the MBCT+TAU group (n = 102) from 14.9 ( $\pm$  9.2) to 10.3 ( $\pm$  7.8) whereas the TAU group (n = 103) showed no change in depression levels (pretreatment: M = 16.2 ( $\pm$  9.4) and posttreatment: M = 16.2 ( $\pm$  9.8). This corresponded to an effect size of 0.5 for reduction of depressive symptoms in patients with recurrent (unipolar) depression (remitted n = 124, currently depressed n = 58). Based on a two-sided test with an alpha of 0.05 and a power of 80%, with an estimated effect size of 0.5, including a design factor of 1 – r2 (0.75), and taking account of a conservative estimate of 40% loss to follow-up, we intend to recruit N = 160 patients (80 per group).

We anticipate that about 25% of the population will have to be excluded due to (hypo)manic symptoms (when exceeding the maximum on the Young Mania Rating Scale) or other exclusion criteria. We further expect about 25% of the eligible patients to be interested in the study.

Approximately 690 BD patients are treated in ProPersona, with 518 (75%) meeting the inclusion criteria, of whom 130 (25%) would probably be interested to participate. The intended number of participants (n = 60) falls comfortably within this estimate. The number of BD patients treated in Dimence is about 900, with 675 (75%) meeting the inclusion criteria, of whom 169 (25%) would probably be interested to participate. Again, the intended number of participants (n = 50) falls well within this estimate. Approximately 650 BD patient are treated in Altrecht, with 100-150 new patients per year. About 487 (75%) of BD patients would be meeting the inclusion criteria, of whom 122 (25%) would probably be interested. The intended number of participants (n = 50) therefore seems feasible. Moreover, we will recruit patients through the patient association Vereniging voor Manisch Depressieven en Betrokkenen (VMDB) and the psychiatry department of the Canisius Wilhelmina

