## 5. TREATMENT OF SUBJECTS

## 5.1 Investigational treatment

## Mindfulness Based Cognitive Therapy (MBCT) + TAU

This intervention will consist of usual care, with MBCT in adjunct. MBCT is a manualised group skillstraining program (Segal, Williams, & Teasdale, 2012) designed as a relapse prevention programme for patients with recurrent depression. The training consists of eight weekly sessions of 2.5 hours, plus one day of silent practice. In addition, participants are instructed to practice 45 minutes a day. The program includes both formal and informal meditation exercises. Cognitive techniques that are part of the program include psychoeducation, monitoring and scheduling of activities, identification of negative automatic thoughts and devising a relapse prevention plan. The MBCT intervention offered in the current study will be based on the 8-week MBCT course developed by Segal et al. (2012), but will be adapted to address the needs of BD patients. A few examples of these adaptations are as follows: psychoeducation about manic symptoms in addition to psychoeduction about depression; introducing the 3-minute breathing space earlier in the programme and more often during sessions, especially when strong emotions are present; repeatedly bringing the focus to self-care; and making use of the mindful movement (yoga) exercises more frequently. All group sessions will be conducted at the respective mental health sites, with each group comprising 8 - 12 participants.

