## 6.3 Study procedures

Figure 2 provides a flowchart of the study procedures from referral to the final assessment. Patients will be recruited from several specialized, outpatient clinics in the Netherlands; ProPersona, Dimence, and Altrecht, and through the patient association; Vereniging voor Manisch Depressieven en Betrokkenen (VMDB). They will receive a letter from their attending clinicans, informing them about the study with an included information leaflet. This way, patients are free to choose whether to participate in the study, without feeling obligated to their clinicans when asked face-to-face. Interested patients are, after verbal consent is obtained, invited for a screening by telephone to assess global eligibility. Eligible patients will receive more information and a detailed description of the study procedure. After one week, patients will be contacted by telephone to assess whether they are still interested in participation. Patients who are still interested to participate will be invited for intake with a research assistant, where informed consent is obtained. They are thoroughly screened for in- and exclusion criteria with use of the SCID-I and YMRS. Altogether, this will take about 1.5 hours. When patients are still eligible and interested, they are invited for baseline assessment (T0), which consists of several clinician administered measures (IDS-C and FAST), which will take about 20 minutes. After a short pause, participants are asked to conduct five short computer tasks (Stroop, Emotional Stroop Task, Breathing Focus Task, Self Referent Encoding Task, and Attentional Control Scale). This will take about onee hour. However, it is possible for participants to do only the first part of these measures, so they can skip the computer tasks if necessary. Furthermore, participants are asked to fill in several self-report questionnaires at home (STAI, brooding subcale of RRS, CHIME, SCS-SF, MHC-SF, RPA, CTQ, TiC-P, and EQ-5D-5L). After baseline assessment, patients are randomised to one of two groups: TAU or MBCT + TAU. Participants in the intervention group (MBCT + TAU) will receive an eight-week MBCT training, during which they daily have to document mood fluctuations, changes in medication, and major life events in the Life Chart. Furthermore, participants are asked to document adherence and adverse events in a personal diary. Participants in the comparator group (TAU) will receive their treatment as usual, while they daily document in the Life Chart as well. After three months (T1), participants are invited for follow-up assessment, during which the clinician administered questionnaires (YMRS, IDS-C, FAST, SCID-I) and computer tasks will be conducted again. Furthermore, patients are asked to fill out the online self-report questionnaires a second time. More follow-up assessments will take place after 6 months (T2), 9 months (T3), 12 months (T4), and 15 months (T5). During T2, T3, and T4 assessments patients are approached by telephone to assess depressive, manic, and anxiety symptoms, and global functioning over the past three months (IDS-C, YMRS, FAST, and SCID-I to assess manic and depressive symptoms retrospectively). Furthermore, during these assessments patients are asked to fill out the online questionnaires as well. The assessment at 15 months follow-up (T5), will consist of the clinician adminstered meassurements (IDS-C, YMRS, FAST) and the online self-report measurements (STAI, brooding subcale of RRS, CHIME, SCS-SF, MHC-SF, RPA, TiC-P, EQ-5D-5L). Table 1 provides an overview of the assessments. After 15 months of follow-up the study will end, after which participants in the comparator group will be given the opportunity to participate in a MBCT-course as well.

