## 8.1 **Primary study parameter(s)**

The primary analysis is aimed at comparing the effects of MBCT + TAU on depressive symptoms. The primary outcome parameter will be the total scores on the IDS-C. In order to investigate consolidation of treatment effect, we will follow-up participants for another 15 months. We will use a multilevel regression model for repeated measures to analyse differences between baseline, 3 months, 6 months, 9 months, 12 months, and 15 months follow-up measurements.

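### Section 8 nests the pre-treatment score in the therapy group, so a constant random group effect drops out of the change-from-baseline contrast and leaves its standard error uncorrected for clustering

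*Protocol*

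**What the plan says.** Section 8 describes a hierarchy with "outcome variables at the pre- and postmeasurements at the lowest level, nested within individuals, nested within treatment groups (for the intervention condition"). It then states: "To account for possible differences between therapy groups, we will add a random group effect". No group-by-time term and no group effect limited to follow-up is mentioned.

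Section 8.1 gives the contrast for the IDS-C: "We will use a multilevel regression model for repeated measures to analyse differences between baseline, 3 months, 6 months" and so on to 15 months. Section 8.2 repeats this for the secondary scores. Baseline is thus one of the repeated outcomes and not a covariate.

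On timing, section 6.3 says: "After baseline assessment, patients are randomised to one of two groups: TAU or MBCT + TAU". Figure 2 places randomisation before T0 instead, but in either order T0 comes before the MBCT sessions.

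Two other places bear on which contrast is meant. Section 6.1.1 says: "The primary endpoint of the study is severity of depressive symptoms at 3 months follow-up (T1"), which is a level at one visit. Section 4.4 multiplies the sample size by 1 - r² = 0.75, the usual factor for a baseline-adjusted comparison.

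**The concern.** MBCT is delivered in groups, and patients who share a group and a teacher may respond alike. Section 8 recognises this and adds a term for it. Such differences can arise only once the course has begun. A single group effect shared by T0 and T1 instead describes a group that is equally high or low before and after treatment, and that part disappears when T0 is subtracted from T1. What remains, the variation between groups in response, is then absent from the standard error.

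At stake are the confidence interval and type I error of the primary IDS-C comparison and of the scores in section 8.2. The report would say that clustering had been handled when, for that contrast, it had not.

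**Working it through.** **1. The plan's own figure.** Section 4.4 gives: "Based on a two-sided test with an alpha of 0.05 and a power of 80%, with an estimated effect size of 0.5". The standard two-sample calculation gives 63 per arm. Then 63 × 0.75 = 47.25, rounded up to 48, and 48 / 0.60 = 80 per arm, N = 160. The stated size is reproduced. The factor 1 - r² = 0.75 implies r = 0.5, and the plan expects 48 completers per arm.

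**2. Number of therapy groups.** The site targets in section 4.4 are 60, 50 and 50. Split 1:1, that is 30, 25 and 25 MBCT patients. Section 5.1 describes sessions "with each group comprising 8 - 12 participants". Three groups per site fit this range; two would be too large (25 / 2 = 12.5) and four too small (30 / 4 = 7.5). That makes 9 groups, assuming groups are filled within sites.

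**3. The model as written.** Score = fixed effects + group effect g + person effect u + residual e, with g and u constant over visits. In T1 - T0 both g and u vanish. With total variance 1 and r = 0.5, the variance of a change score is 2(1 - 0.5) = 1, so the standard error of the difference in change is √(2/n):
- n = 80 per arm: √(2/80) = 0.1581 SD
- n = 48 per arm: √(2/48) = 0.2041 SD

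Exact generalised least squares at 80 per arm gives 0.1581 for group variances of 0, 0.01, 0.05, 0.10 and 0.15 alike, with two or six visits. In nine REML fits to simulated data the interaction standard error was the same to four decimals with and without the group intercept. In one data set it was 0.1526 both ways, while a group-by-post term gave 0.1829.

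**4. The true standard error if groups differ only after T0.** Let ICC be the share of post-baseline variance that lies between MBCT groups (not in the protocol, so a range is shown).

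Variance = 2/n + ICC × (1/9 - 1/n)

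True SE / model SE = √{1 + ICC × (n/9 - 1)/2}

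Type I error ≈ 2[1 - Φ(1.96 / ratio)]

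| n per arm | ICC | Ratio | Type I, formula | Type I, simulated |
|---|---|---|---|---|
| 48 | 0.02 | 1.02 | 5.5% | 5.4% |
| 48 | 0.05 | 1.05 | 6.3% | 6.5% |
| 48 | 0.10 | 1.10 | 7.6% | 7.6% |
| 80 | 0.02 | 1.04 | 5.9% | 5.9% |
| 80 | 0.05 | 1.09 | 7.3% | 7.2% |
| 80 | 0.10 | 1.18 | 9.7% | 9.6% |

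Example: n = 48, ICC = 0.05 gives √(1 + 0.05 × 4.333/2) = √1.108 = 1.05. With eight groups of ten instead of nine, the simulated type I error at 80 per arm is 6.0%, 7.7% and 10.3%. At ICC 0 it is about 5%.

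**5. Loss to follow-up.** If 40% of patients have T0 only, the standard error without a group term is √{2(0.75/48 + 0.25/80)} = 0.194. Adding the constant group term gives 0.193. The cancellation is no longer exact, but there is still no correction.

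**6. Other contrasts from the same model.** For the plain arm difference at T1 (80 per arm, nine groups), the model standard error is 0.158, 0.164, 0.173 and 0.187 at ICC 0, 0.02, 0.05 and 0.10, so the group term does enter. With the two arms' baseline means constrained equal it enters in part: 0.137 rises to 0.141 at ICC 0.05.

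**The case against.** The strongest reply is that the protocol does not fix the model that cancels. The nesting sentence describes the data hierarchy and is not an equation. A random group effect could be allowed to vary by visit. Section 8.1 can be read as a list of measurement occasions, with no arm-by-visit coefficient named as the primary test. Section 6.1.1 names a T1 level and section 4.4 uses a baseline-adjusted factor. For a T1 arm difference the group term raises the standard error by the same ratios as in the table, and such detail is commonly left to a SAP.

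Much of this stands. A reader might infer that the plan gives no clustering correction at all, or that its false-positive rate does exceed 5%. The documents support neither statement without conditions. The first depends on a constant group effect and a change contrast with free baseline means. The second also needs a non-zero post-baseline group variance, which the protocol does not quantify. The larger ratios, up to 1.18, also assume no loss, although the plan allows for 40%.

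The reply does not remove the point. Section 8 explicitly puts the pre-score inside the therapy group, and sections 8.1 and 8.2 make baseline one of the outcomes compared. Following that text literally defeats the purpose given for the group term. Turning to the T1 difference is not a full answer either: if group effects arise only after T0, a constant intercept would tend to underestimate them, so the correction may be incomplete.

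**Conclusion.** The point holds conditionally. If the model is fitted as written, with a group effect constant over time and treatment tested as arm-by-visit change, the standard error of that contrast receives no correction for therapy-group clustering. Separately, the analysis text fits neither the T1 endpoint nor the baseline-adjusted factor behind the sample size.

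The size is modest at the planned number of completers: over assumed ICCs of 0.02 to 0.10, the true standard error is about 2% to 10% above the model's and type I error is about 5.5% to 7.6%. With no loss the excess is about 4% to 18%. These figures rest on nine groups, r = 0.5 and group effects that begin after T0. If groups do not differ, there is no inflation. The specification should be corrected before analysis, but the point does not call the design into question.

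**What to change.** In section 8, specify one of two models and name the T1 arm comparison as the primary test:
- T0 as a covariate, T1 to T5 as outcomes, and a random therapy-group effect in the MBCT arm only. This also matches the 1 - r² factor in section 4.4.
- T0 kept as an outcome, with the group effect set to zero at T0 and acting only on post-baseline visits.

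In either model, treat TAU patients, and MBCT patients who never join a group, as clusters of one. Use small-sample degrees of freedom, because there are only about nine groups. Apply the same specification to the scores in section 8.2.

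The cost is a change of wording, with no new data or patients. If groups do differ, intervals become wider, by roughly the ratios in the table for the change contrast. Section 4.4 makes no allowance for this, so some power would be lost.
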